Dose Finding. Escalating dosages of intranasal ketamine will be given during the study in order to find optimal analgesic dose without significant side effects. On the first study visit, after obtaining written informed consent, 10mg of intranasal ketamine will be given to make sure that the study patients are able to tolerate a small dose of NAS ketamine. On the second visit, 10 mg of IV ketamine will be given to help establish bioavailability of NAS ketamine, with patients serving as their own controls. On the third and fourth visit, higher doses of ketamine, 30 mg and 50 mg respectively, will be given, if the patients did not have severe adverse events with the smaller dosage. Licensed study personnel delegated to do so, will administer ketamine. The intranasal ketamine will be administered as follows: 1) Ensure mucosal atomization device (MAD) is primed and the appropriate dose loaded into the syringe. 2) Have patient sit in chair and clear sinuses using a tissue if needed. 3) Tilt the patient's head back. 4) Insert MAD into nostril and aim directly posterior, level with the floor of the nare, and slightly lateral. 5) Administer 0.1mL (10mg). 6) Have patient keep his head tilted back for 5 minutes, if tolerable, to ensure that the medication does not run out of nares. Make a note if medication is visibly noted to run out of nares or if patient reports feeling of medication trickling down his throat. 7) If more than 0.1mL (10mg) needs to be delivered, repeat steps 3-5 in the contralateral nare, alternating until the full dose is delivered. Ensure 30 seconds have passed before re-administration into the same nare. Patients may continue to take their usual pain medication as needed. Since most of the oral immediate release opioid medications peak between 30 to 90 minutes, ketamine will be given at least 120 minutes after the last dose of immediate release opioid medication so the reduction in pain score is not confounded with the results of immediate release opioid medications. Pain scores will be recorded on NPRS prior to and at 5, 10, 15, 30, 45, 60, 120, and 180 and 240 minutes after administration of test medication. NPRS is the most responsive tool to document pain intensity when compared to Visual Analogue Scale (VAS) and Visual Rating Scale (VRS) for measuring pain,²⁹ showing higher compliance rates, better responsiveness, ease of use, and good applicability relative to VAS/VRS³⁰. In general, improvements of pain severity</=1.5 points on NPRS could be seen as clinically irrelevant³¹⁻³⁴. Above that value, the cutoff point for "clinical relevance" depends on patients' baseline pain severity, and ranges from 2.4 to 5.3³³⁻³⁵. Higher baseline scores require larger raw changes to represent clinically important differences³⁶.

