Respiratory effects: Respiratory depression is rare (ventilator response to CO₂ is maintained). Upper airway skeletal muscle tone is maintained; upper airway reflexes remain relatively intact. Respiratory depression can occur when ketamine is given in conjunction with other agents (e.g. opioids) or when given in large doses or rapid infusions. Treatment may include: decrease/stop opioids and other sedating medications. If respiratory depression (RR < 10/min, O₂ sat < 90%) persists at the end of the study visit, the study MD will be notified and potential admission will be considered, the patient's will be admitted for 23 hour observation with the inpatient oncology service.

Ocular effects: Nystagmus (especially vertical nystagmus), diplopia, blurred vision and slight elevation in intraocular pressure are possible. If this happens at the end of the study visit, the study MD will evaluate for safeness for discharge vs 23 hrs observation.

Musculoskeletal effects: There is a possibility of increased skeletal tone or tonic-clonic movements. The study MD notified if this happens. This will be monitored and treated appropriately. Short acting benzodiazepines like IV midazolam may be considered.

Allergic reaction: Ketamine does not evoke histamine release; and, rarely, if ever causes allergic reaction. If an allergic reaction is suspected then the reaction will be treated based on the severity, with steroids and antihistamine allergic agents.

C.6 Benefits:

The patient may benefit from improved pain control and improved mood or depression control by participating in this research study.

C.7 Participant selection:

A sample size of 7 from a population of 20 (in the study done by Carr et al.) achieves 91% power to detect a NPRS difference of -2.7 between the null hypothesis mean of 0.0 and the alternative hypothesis mean of 2.7 with an estimated standard deviation of 1.9 and with a significance level (alpha) of 0.05000 using a two-sided Wilcoxon test assuming that the actual distribution is normal.

We need a sample size of 7 patients based on statistical analysis observed in the study done by Carr. We will include 10 patients to account for the possibility that the observed pain reduction in the current study may be different than the study done by Carr, as in this study patients were given ketamine for breakthrough pain,

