as opposed to for baseline pain. We will enroll up to 25 patients in the study to account for potential dropouts. If a higher dropout rate is observed, then we will enroll more patients until we have at least 10 patients who complete the entire study.

Subject Replacement

Any subject who does not complete the IV dosing and at least one intranasal dose will be replaced and followed for safety as needed and/or via telephone call at 14 days.

Enrolled subjects who discontinue early will be replaced.

If a subject misses more than one treatment visit during the study period, the subject will be withdrawn and replaced to achieve a minimum of 10 subjects who are maximally treated with study medication (4 study visits).

The patients should meet the following inclusion and exclusion criteria.

C.8 Inclusion Criteria: Patients will be eligible to participate if they are:

1. Male and female subjects at least 18 years of age
2. Patients with uncontrolled pain related to cancer or cancer treatment. Uncontrolled pain will be defined as ^{46,47}
 - i. pain which persists for more than 7 days and is rated $>/=4$ on NPRS
 - ii. use of breakthrough medication more than 4 times in 24 hours or being treated with oral morphine equivalent of 50 mg/d or more
3. Patients who are⁴⁸ able to follow-up in person during the trial
4. Patient on stable analgesic regimen for >7 days without escalation during study period with rescue or immediate release medication every 3 hours or longer
5. Patients who are willing and able to maintain a daily pain diary
6. Patients who are able to understand written and verbal English
7. Patient weight $>/= 50$ kg

C.9 Exclusion Criteria: Patients will be excluded from the study if they have any of the following:

1. Transportation issues interfering with return study visits
2. Patients with high disposition of laryngospasm or apnea
3. Presence of severe cardiac disease

4. Presence of conditions where significant elevations in blood pressure would be a serious hazard.
5. Stage 2 hypertension or greater (systolic blood pressure > 160 and/or diastolic blood pressure >100)
6. Baseline tachycardia, HR >100
7. History of seizures, elevated ICP or CSF obstructive states(e.g. severe head injury, central congenital or mass lesions)
8. Conditions that may increase intraocular pressure (e.g. glaucoma, acute globe injury)
9. History of uncontrolled depression or other psychiatric comorbidity with psychosis
10. History of liver disease

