2. Determine pharmacodynamics of intranasal ketamine in terms of Patient Reported Outcomes

- i. Pain scores on NPRS will be analyzed by Wilcoxon signed-rank test as the study sample size is too small to be analyzed by paired t test. Generalized Linear Model will be used to model any time trend for pain score change and to test if the trend is significant.
- ii. T-test will be used to compare any changes in depression severity on MADRS.
- iii. Chi-square test will be used to test presence/absence of any side effects. Wilcoxon signed rank test will be used to assess the severity of all the side effects (including SERSDA), if needed.
- iv. Paired T-test will be used to asses any changes in functional status on PROMIS scale.
- v. T-test will be used to compare any changes in ESAS and ECOG.

3. Determine PK-PD relationships of NAS ketamine delivered

Timing, degree and duration of change in pain scores will be compared with individual and group pharmacokinetic parameters to assess potential relationships between measures of exposure (C_{max} , and AUC_{0-t}) and pain relief. Multivariate modeling including patient-specific data (age, sex, weight, BMI, morphine equivalents) will be performed using initial PK parameters and goodness of fit analyses for compartmental model selection. If applicable, data from vital sign measurement changes will also be used as comparison with pharmacokinetic data.

4. Determine opioid sparing effect of intranasal ketamine.

- i. Chi-square test will be used to compare frequency of rescue medication use.
- ii. T-test will be used to compare total opioid consumption.

C.13 Data and Safety Monitoring and Reporting Plan:

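### Must the plan name the dose, reading or summary that carries the sized NPRS Wilcoxon test?

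*Combined protocol and SAP*

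**What the plan says.** C.7 Participant selection takes seven patients to give 91% power, "with a significance level (alpha) of 0.05000 using a two-sided Wilcoxon test". The effect is set "between the null hypothesis mean of 0.0 and the alternative hypothesis mean of 2.7" with an SD of 1.9, and the target is then raised to 10 completers. C.7 does not say at which dose or time the change of 2.7 is measured.

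C.12 item 2.i states the analysis: "Pain scores on NPRS will be analyzed by Wilcoxon signed-rank test as the study sample size is too small" for a paired t test. It adds a second NPRS analysis: "Generalized Linear Model will be used to model any time trend for pain score change and to test if the trend is significant". Neither sentence names a dose, time point or summary. Nothing says which of the two carries the 0.05, and no section gives a multiplicity rule.

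The data are rich. Under Dose Finding in C.2, "Pain scores will be recorded on NPRS prior to and at 5, 10, 15, 30, 45, 60, 120, and 180 and 240 minutes" after dosing. This applies at the 10, 30 and 50 mg intranasal visits and at the 10 mg IV visit. The first visit is described as a tolerability step: "10mg of intranasal ketamine will be given to make sure that the study patients are able to tolerate a small dose of NAS ketamine". On analgesics, "Patients may continue to take their usual pain medication as needed", with at least 120 minutes required between an immediate-release opioid and ketamine. On missed visits, C.7 Subject Replacement says: "If a subject misses more than one treatment visit during the study period, the subject will be withdrawn and replaced".

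**The concern.** A test sized at 0.05 should correspond to one identifiable comparison. Here one test, three tests (one per intranasal dose), 18 (the 30 and 50 mg readings) or 27 (all intranasal readings) would all fit the text. The study is open-label, so the choice could be made after the scores are seen. A reader shown a significant drop at one dose and minute could not tell whether it was the sized comparison or the best of many. The choice of summary could also move power, because an average over four hours dilutes a short-lived effect. The Objectives section says the results will inform a later effectiveness trial, so a selected result could carry forward.

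**Working it through.** **1. The plan's own figure.** Inputs from C.7: n = 7, population 20, difference 2.7, SD 1.9, two-sided 0.05. The Wilcoxon adjustment gives 7 × 3/π = 6.68, truncated to 6. With a finite population correction, SD = 1.9 × √(1 − 6/20) = 1.590. The noncentrality is √6 × 2.7/1.590 = 4.16, and noncentral-t power is 0.909, which matches 91%. The correction treats the 20 patients of the cited breakthrough-pain trial as the population sampled, which does not suit a new sample. Without it, exact signed-rank power is about 85% at n = 7. At the planned n = 10 it is about 97%.

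**2. Number of possible tests.** Three intranasal visits × 9 post-dose readings = 27. Two visits × 9 = 18. One summary per intranasal dose = 3.

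**3. False-positive risk if every reading were tested at 0.05 with no effect.** Were the tests independent, 1 − 0.95^27 = 75.0%. Readings within a visit are correlated, and the documents give no correlations, so two sets of assumptions were simulated at n = 10:
- Within-visit correlation 0.5 to 0.9 and between-dose correlation 0 to 0.5: 33% to 63%.
- Integer scores with change SD 1.9, several within-visit structures and between-visit correlation 0 to 0.9: 18% to 46%, of which 9% to 25% for at least one false pain reduction.

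Three independent tests would give 1 − 0.95^3 = 14.3%. One test chosen in advance has a nominal 5%.

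**4. Would all 27 be tested and adjusted?** The smallest two-sided signed-rank p at n = 10 is 2/2^10 = 0.00195. The Bonferroni level is 0.05/27 = 0.00185. No single reading could ever reach it, so full adjustment is not workable. The realistic options are one contrast or a small family.

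**5. Power of those options** (n = 10, mean change 2.7, SD 1.9, exact signed-rank test):

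| Family | Strictest level | Power per dose |
|---|---|---|
| One contrast | 0.05 | 97% |
| Two doses, Holm | 0.025 | 91% |
| Three doses, Holm | 0.05/3 | 87% |

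**6. Effect of the summary window.** Assume relief rises linearly to 2.7 by 10 minutes and holds to 60.
- Area to 60 minutes: 3.375 + 10.125 + 50 × 2.7 = 148.5. The mean is 148.5/60 = 2.475, and power is 94%.
- If relief is gone by 120 minutes, the 0–240 mean is (148.5 + 60 × 2.7/2)/240 = 229.5/240 = 0.956, and power is about 28%.
- If relief holds to 240 minutes, the mean is (148.5 + 180 × 2.7)/240 = 634.5/240 = 2.644, and power is about 97%.

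All three hold the SD at 1.9, although an average over time need not have that SD. A1 Background says the cited trial stopped recording at 60 minutes, so the documents cannot choose between the last two cases.

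**The case for a change.** The best argument for a change is that the sponsor chose a powered 0.05 test, lists patient-reported outcomes under its primary heading, seeks the best analgesic dose and will carry the findings into a later trial. Naming a contrast costs only wording. Scores are visible as they accrue, because C.13 has investigators review clinical data monthly. The time-trend model does not close the gap, since it names no dose either.

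Part of this stands. The omission is genuine, nothing elsewhere fills it, and a p-value from a dose and minute picked afterwards should not be presented as the sized test.

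The rest is weaker. The high error rates need an analyst to test every reading and report the best one as if it were alone, which the plan does not direct. The fall in power to 28% depends on one assumed relief profile, and the opposite profile gives about 97%. Holm adjustment lowers power per dose from 97% to 91% or 87%. Restricting the 0.05 to NPRS would also demote other outcomes that the Objectives list as primary. That is a choice between aims. Patient set and analgesic use are separate omissions, and the text narrows both. C.7 replaces early discontinuers and enrols until at least 10 patients complete everything. C.2 separates ketamine from the last immediate-release opioid, and C.3 records rescue use.

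**Conclusion.** No change to the plan is needed. This is missing detail that an analyst can fill sensibly. The usual course is to fix one summary at one intranasal dose as the sized comparison before looking at the scores, and to report the other readings, the trend model and the IV visit descriptively. The scheduled readings support that choice without new data or more patients. Power for it is about 97% at 10 completers if its mean change is 2.7 and its SD 1.9.

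Little hangs on the p-value. The study has no control arm, as C.14 acknowledges, and dose rises with visit order. Even a perfectly specified test could not separate drug effect from expectation, regression to the mean or time. A later trial would draw on the size and course of the pain change, its variability and its tolerability, and every visit supplies these whichever contrast is tested.

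The 18% to 63% range is a conditional illustration that rests on assumed correlations and on testing all 27 readings. The 28% to 97% power range for a four-hour summary rests on an unknown duration of relief and a fixed SD. Neither shows that a rule stated in the plan gives a wrong answer.

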2. To evaluate (pharmacodynamic) effects of NAS ketamine on Patient Reported Outcomes (PROs), such as pain scores, side effects, depression, health-related quality of life, and functional status.

2a. To assess PROs as measured by the Numerical Pain Rating Score (NPRS), Side Effect Rating Scale for Dissociative Anesthetics (SERSDA), Montgomery Asberg Depression Rating Scale (MADRS), and Edmonton Symptom Assessment (ESAS), Eastern Cooperative Oncology Group (ECOG) and Patient-Reported Outcomes Measurement Information System (PROMIS) scales.

Secondary Outcomes

3. To determine opioid sparing effect of NAS ketamine.

[figure not shown]
3a. To document use of rescue medications prior to and during the study

3b. To evaluate total opioid consumption prior to and during the study.

If intranasal ketamine can be utilized for pain control in cancer patients, this could provide them with superior analgesia and better quality of life, without the risk of significant respiratory depression associated with opioid medications. We seek to obtain preliminary data via a clinical trial addressing safety, feasibility, and utility of this novel technique for the treatment of persistent uncontrolled cancer pain. These findings would be an important initial step towards testing the effectiveness of intranasal ketamine as a non-opioid medication for cancer pain used as potential maintenance outpatient therapy. These initial findings would be applied to a subsequent trial to determine the effectiveness and associated toxicities of ketamine in a larger sample of cancer patients, and address the compelling need to identify new, successful management therapies for cancer pain.

C.APPROACH:

C.1 Study design and methods:

C.2 Methods:

This is a prospective clinical trial to investigate the use of intranasal ketamine in patients with uncontrolled pain related to cancer or cancer treatment. The trial will be conducted in the Phase 1 Unit of the Winship Cancer Institute (WCI).

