7. The Emory University School of Medicine Department of Anesthesiology will conduct this study according to national rules, regulations and guidelines governing human clinical research. In addition,

procedures cited by the US Code of Federal Regulations (Title 21) will be followed as these apply to the principles of Good Clinical Practice and approval by the Emory University Institutional Review Board (IRB).

Confidentiality: The privacy of the research subjects will be ensured through the standard procedures for securing research data. All records identifying the subject will be kept confidential and, to the extent permitted by the applicable laws and regulations, will not be made publicly available. Subjects will be identified by a study number. If the results of the study are published, the subject's identity will remain confidential.

C.14 Potential Pitfalls:

Lack of blinding/Lack of placebo arm. There is enough evidence to support an analgesic effect of ketamine. Since the study is being conducted in cancer pain patients and involves blood draws and transport, a placebo arm is considered to be unethical in these circumstances. The possibility exists that **ketamine might have long term effects beyond its duration of action** and the pain scores might be significantly lower than the compared to at the beginning of the study. In this case **change in pain score may not be significant during the later study visits**. However, overall this would be a good effect for pain control and can future studies can be designed to account for this effect. As cancer pain can be evolving and changing, the decision was made to finish all the study visits in the least possible duration of time, as possible. Once feasibility and safety is established with this study, the aim of future studies will be allow patients to take this medication at home for maintenance. **Lack of standard opioid regimen** among patients could be problematic in terms of comparison of outcomes.

E. REFERENCES/BIBLIOGRAPHY

1. van den Beuken-van Everdingen, M. H. *et al.* Prevalence of pain in patients with cancer: a systematic review of the past 40 years. *Ann Oncol* **18**, 1437-1449, doi:10.1093/annonc/mdm056 (2007).
2. Malinovsky. Ketamine and norketamine plasma concentrations after i.v., nasal and rectal administration in children. *Br J Anaesth* , 77(72):203-207 (1996 Aug;).

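### The NPRS time trend is to be tested with a Generalized Linear Model with no stated within-patient term, so its p-value can err in either direction (minor; confined to the trend claim)

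*Combined protocol and SAP*

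**What the plan says.** Pain is a Primary Outcomes aim (Objectives, aim 2): "To evaluate (pharmacodynamic) effects of NAS ketamine on Patient Reported Outcomes (PROs), such as pain scores". C.12 item 2.i gives it two analyses. The first is a paired test: "Pain scores on NPRS will be analyzed by Wilcoxon signed-rank test as the study sample size is too small to be analyzed by paired t". The second concerns time: "Generalized Linear Model will be used to model any time trend for pain score change and to test if the trend is significant".

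The scores behind both come from C.2 (Dose Finding), the Table of Assessments and C.3, which set NPRS "prior to and at 5, 10, 15, 30, 45, 60, 120, and 180 and 240 minutes after administration of test medication". That is a baseline and 9 post-dose scores per dosing visit. Visits 1 to 4 are dosing visits: 10 mg nasal, then 10 mg IV, and then "On the third and fourth visit, higher doses of ketamine, 30 mg and 50 mg respectively, will be given", provided the smaller doses caused no severe adverse events. C.7 continues enrolment "until we have at least 10 patients who complete the entire study".

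No section gives a patient effect, a working correlation, a repeated-measures covariance or a robust variance for the trend model. C.2 (Pharmacokinetics) plans a within-subject comparison, but for plasma concentration curves only. C.12 item 3 lists patient covariates for PK-PD modelling and does not address the NPRS trend. Nor does item 2.i say whether the trend runs over minutes within a visit or over visits.

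**The concern.** Scores from one patient over four hours are not independent. A Generalized Linear Model in its usual form takes its standard error from all scores as if each came from a different person. That standard error is wrong in a direction that depends on how patients differ. If they differ only in level, the between-patient spread swells the residual variance although it does not disturb the slope, and a real trend can be missed. If their time courses differ, or neighbouring scores move together, the slope is less certain than the model believes, and a trend can be declared by chance.

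At stake is any statement that relief builds, lasts or fades. The signed-rank test in the same item names no trend contrast, so this model is the only stated trend test. The across-visit reading is also live: C.14 foresees that the "change in pain score may not be significant during the later study visits". A within-patient term is needed on either reading.

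**Working it through.** **The plan's own figure.** There is none for the trend test. The one power figure, 91% at n = 7 in C.7 (difference 2.7, SD 1.9, two-sided 5%), belongs to the Wilcoxon test. It reproduces at 90.9% to 91.3% if the 20 patients of the earlier breakthrough-pain study enter as a finite population. Without that correction power is 87.7% (t test) or 84.5% (simulated exact Wilcoxon). That is a separate matter and does not bear on the trend.

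**Counts.** One dose: 10 × 9 = 90 post-dose scores. Four dosing visits: 90 × 4 = 360. Three intranasal visits: 90 × 3 = 270. The number of independent patients is 10 throughout. The figure of 36 scores per patient (9 × 4) holds only for a fully treated patient, because visits 3 and 4 are conditional.

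**Direction of the error, one dose.** Post-dose times are 5, 10, 15, 30, 45, 60, 120, 180 and 240 min.

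- Σt = 705 and Σt² = 111,275.
- Sxx = 111,275 − 705²/9 = 111,275 − 55,225 = 56,050 min². Divided by 3,600, this is 15.57 h².
- Mean t² = 111,275/9/3,600 = 3.43 h².

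Let patients have level SD a, slope SD b (points/h, running from time zero) and residual SD e. All three are assumed, since the documents give none. To a large-sample approximation, the ratio of the true variance of the pooled slope to the variance that the independence model reports is

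R = (e² + 15.57 b²) / (a² + e² + 3.43 b²),

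and the test rejects a true null with probability about 2Φ(−1.96/√R). With e = 0.7 (e² = 0.49):

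| a | b | R | Rejection at nominal 5% |
|---|---|---|---|
| 1.0 | 0 | 0.49/1.49 = 0.33 | 0.1% |
| 1.0 | 0.3 | 1.89/1.80 = 1.05 | 5.6% |
| 1.0 | 0.6 | 6.10/2.73 = 2.23 | 19% |
| 1.9 | 0.3 | 1.89/4.41 = 0.43 | 0.3% |
| 1.9 | 0.6 | 6.10/5.34 = 1.14 | 6.7% |

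R exceeds 1 when b > a/√(15.57 − 3.43) = a/3.48. That means slopes differing with an SD above 0.29 points/h if a = 1.0, or above 0.55 points/h if a = 1.9. Below that the test is conservative.

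**Simulation.** This also carries the small-sample noise in the residual variance. It used 10 patients, one dose, no true trend and 10,000 trials per setting, with residual SD 0.7 or 1.0, or serial correlation with a 60-minute constant. Rejection by the independence model was:

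- patients differ only in level (SD 0.5 to 1.9): 0% to 3%;
- slopes differ (SD 0.3 to 0.6) with level SD 0 to 1: 6% to 32%; with level SD 1.9: 1% to 10%, or up to 11% in other runs;
- serial correlation with level SD 0 to 1: 3% to 19%; with level SD 1.9: 0.2% to 4.7%;
- time as a category instead of a line: 0% to 7%.

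If slopes pivot at the mean time instead, the upper end at level SD 0 to 1 rises to 41%. Pooling all four visits, with each patient keeping the same slope at every visit, gave 0.05% to 48% over the assumed correlation structures. More patients do not cure it: with n = 25 the differing-slope range is still 6% to 31%.

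**Alternatives, one dose.** Per-patient summaries held 4.4% to 5.7%. A model with a patient intercept alone held 4.7% to 5.1% when only levels differed, but rejected in 15% to 40% with differing slopes or serial correlation.

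**The case against.** The strongest reply is that this is under-specification, not a shown error. C.12 is a short list of tests, and one clause naming a model family does not commit the analyst to independence; a fit by estimating equations or with patient terms would still bear the name. That stands. The point is what the text permits, not what the trial will certainly do.

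A reader might infer that the trend test is inflated and will produce false trends. The documents do not support that. The only NPRS SD they give is 1.9 (C.7), and near that value the test is often conservative. With the total SD held at 1.9 it rejected in 0.2% to 16%, exceeding 5% only at a slope SD of 0.45 points/h or more, or at the strongest serial correlation tried. That anchor is itself an assumption, because the 1.9 comes from another trial.

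A reader might also infer that the main pain result is compromised because pain sits under Primary Outcomes. It is not. The signed-rank analysis is paired and is the one sized in C.7; the trend supplements it; no success rule depends on it; and the study seeks preliminary data.

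On remedy, a single early-versus-late contrast would be too narrow for a plan that speaks of any time trend. For relief that builds by 30 minutes and then holds, a contrast of 120–240 min against 10–60 min was detected in 41% of trials, against 81% for a per-patient slope by signed-rank.

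**Conclusion.** The point holds in a limited form. Item 2.i states no within-patient term for a test on heavily repeated scores, and in its standard form the named model can give a wrong trend p-value. It is too conservative if patients differ only in level, and too liberal if their time courses differ enough or their scores are strongly serially correlated.

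The size is unknown, because the documents give no within-patient correlations. Under the main assumed variances (10 patients, one dose) the rejection rate ran from about 0% to 30% at nominal 5%, and from about 0% to 11% at a level SD of 1.9. These are illustrations, not predictions.

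The harm is confined to claims about relief growing or fading. Severity: minor.

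**What to change.** In C.12 item 2.i, state whether the trend is within a visit or across visits, and test it with the patient as the unit.

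- **Within a visit.** Compute one NPRS slope over time per patient at each dose and test it across patients by the Wilcoxon signed-rank test already named. Alternatively, use a mixed model with patient-specific slopes or serial covariance and small-sample degrees of freedom. A patient intercept alone is not enough if slopes differ. One slope per dose means up to four tests, so say how they will be read together.
- **Fading of relief.** An early-versus-late contrast is suitable only if fading is the stated question.
- **Across visits.** Use one slope over visits per patient, tested the same way, and state that it cannot be separated from dose and route, which change by visit.

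The cost is a few sentences and slightly more analysis; no new data, visits or patients. There may be less apparent significance. For a true slope of −0.2 points/h with slope SD 0.3, power is about 37% for the per-patient slope by signed-rank, against about 50% for the independence model, whose error rate is then inflated. If slopes are equal (level SD 1.0, residual SD 0.7), the per-patient slope gains instead: 87% by signed-rank against 59%.
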